7.2 Primary Efficacy Analysis

The primary efficacy analyses will use the ITT population and the Primary Wound Pair.

The primary endpoint is the proportion of DEB primary wound sites with complete wound healing from baseline in B-VEC-treated and placebo-treated intra-subject wound sites at Weeks 22 and 24 or 24 and 26, as determined by the Investigator. Complete wound healing is defined as 100% wound closure from the exact wound area selected at baseline, specified as skin re-epithelialization without drainage:

The primary endpoint is defined as responder wounds that meet any of the following conditions:

- Healed on Week 22 and Week 24, or
- Healed on Week 24 and Week 26

Only wounds that are healed for at least two (2) consecutive weeks are counted as positive responses. The primary endpoint response data will be summarized descriptively by the wound treatment.

A summary of the outcomes for each member of the Primary Wound Pair can be represented in the following 2x2 table, where each entry represents a subject. T is the total number of subjects in the ITT population and each cell entry is the number of subjects with the corresponding outcomes of the Primary Wounds.

		Placebo		Row total
		Complete Wound Healing	No Complete Wound Healing	
B-VEC	Complete Wound Healing	A	B	N1
	No Complete Wound Healing	C	D	N2
Column total		M1	M2	T

The null hypothesis of interest is the absence of a treatment effect on wound healing and the alternative hypothesis is the presence of a treatment effect on wound healing.

These hypotheses are equivalent to the following null and alternative hypotheses:

Null Hypothesis H0: Prob(B) = Prob(C)

Alternate Hypothesis H1: Prob(B) ≠ Prob(C)

Where Prob(B) and Prob(C) are the probability of the occurrence of discordant pairs B (B-VEC=Positive & PBO=Negative) and C (B-VEC=Negative & PBO=Positive).

The null hypothesis will be tested by a McNemar test statistic using a two-sided type I error rate of 0.05:

$$\chi^2_{\text{McNemar}} = (B - C)^2 / (B + C)$$

Under the null hypothesis of no difference between the proportions of the two possible types of discordant pairs, this test statistic follows a chi-square distribution with 1 degree of freedom. If the total number of discordant pairs (B+C) are sufficiently small (less than 6), the McNemar test with a continuity correction will be used. If the chi-square test result is significant, the null hypothesis of no treatment difference will be rejected in favor of the alternative hypothesis that a treatment difference exists.

In addition to testing the null hypothesis, the McNemar odds ratio and its 95% confidence interval will be summarized to indicate the magnitude of the treatment effect with B-VEC treatment. The McNemar odds ratio is the ratio of the counts of the discordant pairs B and C.

For subjects with missing primary endpoint data, a multiple imputation approach (details see section [7.1.6](#)) assuming MAR will be used.

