3.1.3 Number of Subjects and Interim Analysis

With 90% power and a two-sided Type 1 error rate of 5%, 24 subjects (i.e., 24 wound pairs) are required for a McNemar's test, assuming a response rate of 75% among wounds randomized to B-VEC and a response rate of 25% among wounds randomized to placebo. These response rates are supported by the results of a Phase 1/2 study in which the response rates for weeks 10 and 12 were 71% and 83% for active and 33% and 14% for placebo, respectively. Because the sample size calculation assumes no correlation within subjects, the estimate is conservative. Any positive correlation will cause an increase in power for the sample size of 24. PASS 2020, "Tests for Two Correlated Proportions (McNemar Test)", was used to calculate the sample size. Because of the small n, the multinomial enumeration was used instead of the normal approximation.

If we assume a 75% response rate among wounds randomized to B-VEC and a 25% response rate among wounds randomized to placebo and we assume independence among the wounds within a subject, we expect a total of 62.5% discordant pairs. Under this scenario, 18.75% of the subjects will have positive responses for both wounds and 18.75% will have negative responses for both wounds:

Expected rates of response and non-response, assuming a 75% response rate for B-VEC treated wounds, a 25% response rate for placebo-treated wounds and no correlation between wounds. The off-diagonals correspond to discordant pairs.

		Placebo		
		Response	Non-response	Total
B-VEC	Response	18.75%	56.25%	75.00%
	Non-response	6.25%	18.75%	25.00%
	Total:	25.00%	75.00%	100%

[figure not shown]
Interim analyses will not be performed for this study.

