When the last variable in the sequence (e.g., the primary efficacy endpoint) has been imputed, the algorithm cycles again through each variable, repeating the chain of regression estimation and imputation draw steps. These cycles are repeated and finally there will be $m=10$ draws from the predictive distribution for each missing primary efficacy endpoint value.

Analyzing multiply imputed datasets

Individual statistical analysis will be performed using the McNemar Test for each of the $m=10$ imputed complete datasets and the results (point estimates and associated standard errors for the study treatment effect) will be stored in a single output file.

Estimation and inference for multiply imputed datasets

As a final step, the $m=10$ estimates and associated standard errors will be combined using the method described on p. 115 of Schafer, J.L. (1997). The chi-square statistics can be either Wald statistics or

likelihood ratio statistics. The chi-square values and the degrees of freedom from all 10 imputed datasets will be used.

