7.3 Key Secondary Efficacy Analysis

The key secondary efficacy analyses will be based on the ITT population. The primary efficacy analyses will be repeated for responder wounds that meet any of the following conditions:

- Healed on Week 8 and Week 10, or
- Healed on Week 10 and Week 12.

Only wounds that are healed for at least two (2) consecutive weeks are counted as positive responses. The key secondary endpoint response data will be summarized descriptively by the wound treatment.

The McNemar testing procedure used for the primary endpoint will be repeated for this key secondary endpoint. A multiple imputation approach (details see section [7.1.6](#)) assuming MAR will be used to impute missing endpoint data. If the primary endpoint is statistically significant at a type I rate of 0.05, the same full type I rate of 0.05 will be passed on to evaluate the key secondary endpoint.

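### The only effect measure with an interval in SAP 7.2, the ratio B/C, is infinite when C = 0: about a 21% event under the plan's own assumptions, with no interval method or zero-count rule

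*SAP*

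**What the plan says.** SAP 7.2 sets out the paired 2×2 table. B is the number of subjects whose B-VEC wound alone healed, C the number whose placebo wound alone healed, and T the total. The null hypothesis is tested with (B − C)²/(B + C). For the size of effect the section names the McNemar odds ratio with a 95% interval: "The McNemar odds ratio is the ratio of the counts of the discordant pairs B and C". The section's one small-count rule is a continuity correction when B + C is below 6. It alters the test statistic, not the estimate. Healed proportions are also to be summarised by treatment, with no interval mentioned.

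SAP 7.3 repeats the primary analyses for Weeks 8 to 12: "The McNemar testing procedure used for the primary endpoint will be repeated for this key secondary endpoint".

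SAP 7.1.6 analyses each of ten imputed datasets, after which the "estimates and associated standard errors will be combined using the method" in a cited text. It adds that the chi-square values from the ten datasets will be used.

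SAP 7.2.1 and 7.3.1 list a risk difference as supplementary, to be obtained from conditional logistic regression stratified by subject.

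SAP 3.1.3 gives the planning assumptions: "With 90% power and a two-sided Type 1 error rate of 5%, 24 subjects (i.e., 24 wound pairs) are required for a McNemar's test", with 75% and 25% response and no within-subject correlation. It then says "we expect a total of 62.5% discordant pairs", which its table splits into 56.25% for B and 6.25% for C. It also notes: "Any positive correlation will cause an increase in power for the sample size of 24".

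**The concern.** A ratio of two counts is a fragile summary when the denominator is expected to be very small. Here the expected C is 24 × 0.0625 = 1.5 pairs. At C = 0 the ratio is infinite, and the usual standard error of log(B/C), √(1/B + 1/C), is undefined. The positive correlation that the SAP links to higher power makes C smaller still when the response rates are held fixed.

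At stake is whether a successful trial can report its primary effect with a pre-specified estimate and interval. The point concerns estimation only, not the decision on the null hypothesis.

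**Working it through.** **Inputs (SAP 3.1.3).** T = 24 pairs; response 75% v 25%; independence; pB = 0.5625; pC = 0.0625; two-sided 5% test; power by multinomial enumeration.

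**Step 1: reproduce the sample size.** Enumerating (B, C) with the two-sided exact binomial McNemar test gives power 0.888 at 23 pairs and 0.905 at 24. So 24 is the smallest number reaching 90%, and the planning table is the right basis for what follows. The test specified in 7.2 (uncorrected chi-square, corrected if B + C < 6) has power 0.941 at 24 pairs.

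**Step 2: chance that C = 0.** C is binomial(24, pC), so P(C = 0) = (1 − pC)^24 = 0.9375^24 = 0.212. Nearly all such trials are significant, because the statistic reduces to B when C = 0. Among significant trials the share with C = 0 is 22.6%.

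**Step 3: vary the assumptions.** With margins fixed at 75% and 25% and within-pair correlation ρ, pC = 0.0625 − 0.1875ρ, where 0.1875 = √(0.75 × 0.25 × 0.25 × 0.75). Since pC cannot be negative, ρ ≤ 0.0625/0.1875 = 1/3.

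| Scenario (24 complete pairs) | pC | P(C = 0) | Power, test in 7.2 |
|---|---|---|---|
| ρ = −0.1 | 0.0813 | 13% | 0.920 |
| ρ = 0 (planning table) | 0.0625 | 21% | 0.941 |
| ρ = 0.1 | 0.0438 | 34% | 0.962 |
| ρ = 0.2 | 0.0250 | 54% | 0.981 |
| Phase 1/2, Week 10: 71% v 33%, independent | 0.29 × 0.33 = 0.0957 | 9% | – |
| Phase 1/2, Week 12: 83% v 14%, independent | 0.17 × 0.14 = 0.0238 | 56% | – |

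Under the planning table, 22 pairs would give 24% and 30 pairs 14%. The documents give no value for ρ, so the correlated rows are illustrations. The Phase 1/2 rows use single-visit rates, not the two-visit endpoint.

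**Step 4: imputation.** A log odds ratio can be pooled only if C > 0 in every imputed dataset. Suppose 3 pairs lack both outcomes. An imputed dataset can have C = 0 only if the 21 complete pairs do, so the chance that any dataset is affected is at most 0.9375^21 = 25.8%, whatever the imputation model.

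**Step 5: what remains computable at C = 0.** Take B = 13, C = 0, T = 24.
- Odds ratio: infinite, with no log-odds interval.
- Exact conditional interval: the lower Clopper-Pearson limit of B/(B + C) is 0.025^(1/13) = 0.753, so the lower limit of the odds ratio is 0.753/0.247 = 3.05. There is no finite upper limit.
- Paired difference: 13/24 = 0.542, with standard error √(B + C − (B − C)²/T)/T = √(13 − 169/24)/24 = 0.102.

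**Step 6: the supplementary analysis.** In 1:1 pairs, conditional logistic regression estimates an odds ratio whose unadjusted value is B/C. It diverges at the same C = 0, and 7.2.1 does not say how a risk difference would be derived from it.

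**The case against.** The strongest reply is that this is a reporting detail. Much of that stands.

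- A reader might infer that the trial could succeed with no reportable size of effect. The documents do not support that: 7.2 reports the 2×2 table and the healed proportions by treatment, so (B − C)/T can be read off whatever C is. What is missing is an interval for it.
- A reader might infer that no 95% interval can be computed. That is true only of the usual log-odds interval. The SAP names no method, and an exact interval with a finite lower limit complies with its text.
- A reader might infer that the primary test or its pooling fails. It does not: at C = 0 the statistic equals B, and 7.1.6 provides for combining chi-square values.
- A reader might infer that the estimate fails exactly when B-VEC works best. Step 3 shows otherwise: at unchanged response rates P(C = 0) moves from 13% to 54% with correlation alone.
- A reader might infer that any substitute measure would be chosen after unblinding. That goes too far, since 7.2.1 names the risk-difference scale in advance. It leaves the route to that quantity unclear, however, so it is not a dependable fallback.

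What the reply does not remove is that the one effect measure given an interval has no zero-count rule, although the SAP's own table makes a zero count quite likely.

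**Conclusion.** The point holds as a gap in estimation. Under the planning table, with 24 complete pairs and independence, about 21% of trials, and about 23% of significant ones, would have an infinite B/C and no usual log-odds interval. The figure depends on pC: 9% to 56% at the quoted Phase 1/2 rates under independence, and 13% to 54% for correlations from −0.1 to 0.2. If a log odds ratio is what is pooled, imputation meets the same obstacle; 7.1.6 does not say which estimate it pools, but 7.2 names no other. The key secondary analysis inherits the gap through 7.3. The hypothesis test and the descriptive results stand, so this is a worthwhile, inexpensive improvement and not a threat to the trial's conclusion.

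**What to change.** In SAP 7.2 and 7.3:

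1. Add the paired difference in healed proportions, (B − C)/T. With complete data, give a 95% score interval for paired proportions (for example Tango's). With imputed data, pool the difference and its standard error by Rubin's rules. This estimate is always finite and matches the endpoint, which is stated as a proportion of wounds healed.
2. Keep the odds ratio, but name its interval: the exact conditional interval from the Clopper-Pearson limits of B/(B + C). State that when C = 0 it is reported as a lower limit only (3.05 for 13 v 0).

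The cost is one extra estimate to report and a few lines of SAP text and code. The test, alpha, sample size and data collected do not change.

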7.2.1 Sensitivity and Supplementary Analyses of the Primary Efficacy Endpoint

Sensitivity analyses of the primary endpoint include:

- The primary analysis described in Section [7.2](#) for the primary efficacy endpoint will be repeated for the PP and mITT populations.
- The primary analysis described in Section [7.2](#) for the primary efficacy endpoint will be repeated with observed data without any imputations for missing values (i.e., if a subject is missing either a B-VEC or placebo outcome, the subject will be excluded from the analysis).

Supplementary Analysis:

- Common treatment risk difference will be obtained from conditional logistic regression with covariates age and gender and stratified by subject (matched pair) and multiple imputation approach described in section [7.1.6](#) assuming MAR.

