3.1.4 Randomization and Blinding

3.1.4.1 Wound Selection

One (1) matched wound pair that meets the inclusion criteria (Figure 2) will be selected to be part of the study. Prior to randomization, wounds will be selected and labeled. The Primary Wounds will be labeled P1 & P2. For each subject, one Primary Wound is randomized to B-VEC and the other Primary Wound is randomized to placebo. Up to four (4) Secondary unmatched wounds may be chosen to receive the Remaining Weekly Dose of B-VEC. Secondary wounds will be labeled as they are selected starting with S1, S2, S3 and S4.

Figure 2. Wound Pairing, Labeling, and Selection Example

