7.1.6 Analysis Methods – Multiple imputation

Multiple imputation methods will replace each missing primary efficacy endpoint value with a set of $m=10$ plausible values based on a model predicting values for a missing data point based on available data, assuming a Missing at Random (MAR) missingness mechanism.

This set of values represents the uncertainty about the correct value to be imputed. Each of the 10 complete datasets (generated by SAS PROC MI) will be analyzed by relevant statistical procedures (e.g., SAS PROC FREQ for McNemar Test, SAS PROC LOGISTIC, etc). The results for the 10 datasets will be combined using the method described on p. 115 of Schafer, J.L. (1997)

Prediction model

The prediction model predicts a missing endpoint value based on available data (variables) that may have an influence on that endpoint. The prediction model for the binary primary efficacy endpoint will be a logistic regression model with the following covariates:

- randomized study treatment: B-VEC or placebo
- sex: male or female
- age at baseline (continuous covariate)
- body weight at baseline (continuous covariate)
- race (White, African American, additional groups must represent at least 25% of the population if not, will group as 'All Other')

Algorithm for the multiple imputation of missing values

Within the Bayesian framework, the task of imputing missing values is achieved by drawing random values from the posterior predictive distribution of the missing primary efficacy endpoint data (predicted by the logistic regression prediction model specified above). This posterior predictive distribution is a function of the observed data and regression parameters (or function of regression parameters).

As non-monotone missing pattern may be observed, the fully conditional specification (FCS) method will be used for dealing with arbitrary non-monotone missing data patterns. The FCS is based on an iterative algorithm; at each iteration and for each variable of the prediction model, there is a

- prediction step (P-step): the current (iteration) values of the observed and imputed values are used to derive the predictive distribution of the missing values
- and an imputation step (I-step): updated imputations are generated by draws from the predictive distribution defined by the updated regression model.

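### SAP 7.2.1 and 7.3.1 promise a risk difference from conditional logistic regression, a model that on 1:1 wound pairs returns only the odds ratio B/C already reported in 7.2

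*SAP*

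**What the plan says.** The design is paired within subject: "For each subject, one Primary Wound is randomized to B-VEC and the other Primary Wound is randomized to placebo" (SAP 3.1.4.1). SAP 7.2 sets out the 2x2 table of pairs. A and D count the concordant pairs, B the pairs in which only the B-VEC wound heals, C the pairs in which only the placebo wound heals, and T all subjects. The test is the McNemar chi-square, with a continuity correction if B+C is below 6. For the size of effect, "the McNemar odds ratio and its 95% confidence interval will be summarized to indicate the magnitude of the treatment effect", and 7.2 defines this measure: "The McNemar odds ratio is the ratio of the counts of the discordant pairs B and C".

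SAP 7.2.1 then adds a supplementary analysis: "Common treatment risk difference will be obtained from conditional logistic regression with covariates age and gender and stratified by subject (matched pair", under the multiple imputation of 7.1.6. SAP 7.3.1 carries the same sentence for the key secondary endpoint, for which 7.3 states: "The McNemar testing procedure used for the primary endpoint will be repeated for this key secondary endpoint".

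Neither section gives a link function, a standardization step or any other route from the fitted model to a risk difference, and neither specifies a treatment-by-age or treatment-by-gender interaction. SAP 7.1.2 says that the efficacy analyses use no covariate adjustment.

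**The concern.** The quantity named and the model specified do not belong together. Conditional logistic regression stratified by pair works on the odds-ratio scale and conditions away everything that is constant within the pair. That includes each subject's overall tendency to heal, without which an odds ratio cannot be turned into a difference in proportions. Age and gender are constant within the pair too: 7.1.6 treats age as a subject-level value, "age at baseline (continuous covariate".

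This is the only analysis that the SAP names on the absolute scale for the two main endpoints. Run as written, it reproduces the odds ratio of 7.2 under another label. If the programmer notices, an estimator and an interval have to be chosen without a prespecified rule, possibly after unblinding. With 24 pairs the choice of interval can decide whether zero is excluded.

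**Working it through.** **Inputs.** SAP 3.1.3: 24 pairs, response rates 75% and 25%, independent wounds. Hence P(B) = 0.75 × 0.75 = 0.5625 and P(C) = 0.25 × 0.25 = 0.0625. SAP 7.2: the 2x2 table, the test rule and the odds ratio B/C.

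**The plan's own figure.** P(B) + P(C) = 0.625, the 62.5% discordance in SAP 3.1.3. Enumerating (B, C) with the exact binomial McNemar test gives power 0.9048 at 24 pairs and 0.8882 at 23, so 24 is reproduced. This point does not touch it.

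**Step 1: what the model estimates.** Let β be the treatment coefficient. A concordant pair contributes a constant to the conditional likelihood. What remains is

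L(β) = [e^β/(1+e^β)]^B × [1/(1+e^β)]^C,

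with its maximum at β = ln(B/C) and SE = sqrt(1/B + 1/C). For B=13, C=2: β = ln 6.5 = 1.872 and SE = sqrt(1/13 + 1/2) = 0.760. Fitting the model to three tables confirms this.

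| A, B, C, D | T | Odds ratio from model | (B-C)/T |
|---|---|---|---|
| 0, 13, 2, 0 | 15 | 6.5 | 11/15 = 0.73 |
| 4, 13, 2, 5 | 24 | 6.5 | 11/24 = 0.46 |
| 12, 13, 2, 13 | 40 | 6.5 | 11/40 = 0.28 |

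One model output goes with three risk differences, so the risk difference is not a function of the fit. T=15 and T=40 are illustrations; the planned T is 24.

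**Step 2: age and gender.** The within-pair difference of each is 0. For B=13, C=2 the conditional log-likelihood is 13 ln(13/15) + 2 ln(2/15) = -5.8901, and it keeps that value whatever coefficients age and gender are given. Neither coefficient can be estimated and neither alters β.

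**Step 3: the quantity named.** The paired risk difference is RD = (B-C)/T, with SE = sqrt(B + C - (B-C)²/T)/T. At the planning table B = 24 × 0.5625 = 13.5 and C = 24 × 0.0625 = 1.5. So RD = 12/24 = 0.50 and SE = sqrt(15 - 144/24)/24 = 3/24 = 0.125. The model's target at the same table is 13.5/1.5 = 9.

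**Step 4: which interval.** Full enumeration at 24 complete pairs and the planning rates gives these results for nominal 95% intervals:

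| Interval for RD | Exact coverage | Tables with T=24, B+C≥6 that disagree with the uncorrected McNemar test |
|---|---|---|
| Wald | 93.1% | 10: (6,1), (8,2), (10,3), (13,5), (16,7) and mirror images |
| Score (Tango) | 94.9% | 0 |

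Example: B=10, C=3, T=24. McNemar chi-square = 49/13 = 3.77, p = 0.052. RD = 7/24 = 0.29 and SE = sqrt(13 - 49/24)/24 = 0.138. Wald gives 0.02 to 0.56, which excludes zero; score gives -0.003 to 0.54, which does not.

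**Step 5: a side note on C=0.** With 24 complete pairs at the planning rates, P(C=0) = (1 - 0.0625)^24 = 0.9375^24 = 21%. B/C is then infinite, while RD is finite. At B=13, C=0, T=24, RD = 13/24 = 0.54, with score interval 0.33 to 0.72.

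**The case against.** The strongest reply is that little depends on this. The analysis is supplementary, the covariate terms do nothing, and anyone can read (B-C)/T off the table in 7.2. That stands as to weight. It does not supply the missing estimator or its interval, and it leaves a sentence, repeated in two sections, that cannot be carried out as written.

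The remedy can be criticised too. The SE pooled over imputations is the Wald SE, whose interval Step 4 shows to be the weaker one, so the ITT interval will be slightly too narrow. And the score interval tracks the uncorrected test, not the full rule of 7.2. At (B, C) = (4,0) and (5,0) the uncorrected p is 0.046 and 0.025, but the continuity-corrected p is 0.134 and 0.074, so below B+C=6 the two can differ. Both criticisms are right and should be stated in the SAP.

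A reader might infer more than the documents support:

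- *That the primary test or sample size is compromised.* Neither uses this model, and the McNemar chi-square stays finite at C=0 (13.0 at B=13, C=0).
- *That C=0 makes the pooling of 7.1.6 fail.* The text says "estimates and associated standard errors will be combined using the method described on p. 115" and also refers to chi-square values. It does not say that log(B/C) is what is pooled, and the cited page is not available here. C=0 is therefore only a further reason to show the risk difference.
- *That the odds ratio needs an exact binomial interval, or should be withheld if C=0.* The exact interval disagrees with the uncorrected test in 16 tables at T=24 with B+C≥6 (probability 3.6% at planning rates). For example, B=9, C=2 gives p=0.035 but limits of 0.93 to 42.8. Withholding a measure that 7.2 promises would be a preference; nothing in the documents calls for it.

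**Conclusion.** The point holds for the supplementary analyses in SAP 7.2.1 and 7.3.1. The specified model yields B/C and cannot yield the named risk difference, and age and gender have no effect in it. Naming them also sits awkwardly with SAP 7.1.2, though with no numerical consequence. This follows from the 1:1 pairing and needs no assumption about response rates. With a treatment-by-covariate interaction the covariates would matter, but none is specified.

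The sizes quoted (0.50 with SE 0.125, coverage 94.9% against 93.1%, and 21% for C=0) rest on the SAP's planning rates, independent wounds and 24 complete pairs. Coverage after pooling over imputations was not computed. The correction is worth making before unblinding, but its weight is modest: the McNemar test, the 24 pairs and the type I error are unaffected.

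**What to change.** In SAP 7.2.1 and 7.3.1:

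1. Replace the conditional logistic model by the paired risk difference (B-C)/T with SE = sqrt(B + C - (B-C)²/T)/T. Compute both in each of the 10 imputed datasets and pool them in the ITT population. Delete age and gender.
2. In the observed-data sensitivity analysis, where "if a subject is missing either a B-VEC or placebo outcome, the subject will be excluded from the analysis" and only complete pairs remain, give a score-type (Tango) paired 95% interval for the risk difference.
3. State the two limits: the pooled ITT interval is of Wald type and slightly too narrow, and for B+C below 6 the continuity-corrected test can differ from the score interval.
4. Report the risk difference beside the odds ratio for both endpoints, since it stays finite when C=0.

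The cost is SAP wording and programming, with no new data, visits or alpha. It should be settled before unblinding.
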